PTQ (Appendix 5g): The *Perseverative Thinking Questionnaire* (PTQ) (Ehring 2011), is a content-independent measure of repetitive negative thinking. The 15 item measure is comprised of three characteristic factors of repetitive negative thinking: (1a) repetitiveness (1b) intrusiveness, (1c) difficult to disengage from (2) unproductiveness (3) capturing mental capacity. The questionnaire has good internal consistency (Cronbach's α =.94; 15) and demonstrable sensitivity to change (Freeman 2015). 15 Items are rated on a 4-point Likert scale (range 0-60; with higher scores indicative of more perseverative thinking). In this study, the rubric of the PTQ will be modified to refer to the "past week" in line with the other emotion regulation measures.

Insomnia severity (Appendix 5e): Participants will complete the Insomnia Severity Index (ISI) (Morin 1993) to quantify global insomnia severity. The ISI is a seven-item insomnia assessment tool, probing both nighttime and daytime aspects of insomnia disorder, and is sensitive to change following CBT-I. It is a recommended outcome measure in insomnia trials (Buysse 2006). The ISI will be supplemented with four items from the Pittsburgh Sleep Quality Index (PSQI) (Buysse 1989) (appendix 5g) to permit calculation of quantitative sleep parameters, namely: total time in bed, sleep-onset latency, total sleep time, and sleep efficiency.

Mood Instability

Changes in mood instability will be assessed using one item (self-rated) from the Structured Clinical Interview for DSM-IV (SCID-II): "Do you often have lots of sudden mood changes?". In this study, the phrasing of the question is altered to refer to the past week. "Over the past week, have you had lots of sudden mood changes?"

Munich Chronotype Questionnaire (MCTQ, Appendix 5j) (Roenneberg et al., 2003) is a 14-item scale assessing the regularity of sleep timing on work days and work-free days. Midpoint of sleep on work-free days, sleep-corrected (MSF $_{\rm SC}$) is calculated from the midpoint of sleep on work-free days minus half of the difference between sleep duration on work-free days and average sleep duration of the week to control for sleep debt.

Positive and Negative Affect Schedule - Short Form (PANAS-SF, Appendix 5k) (Watson et al., 1988)

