- 1. dCBT-I will improve objective biases in negative emotional processing of faces relative to Sleep Hygiene Education (SHE) (5 weeks post randomisation)
- 2. dCBT-I will improve objective negative biases in categorization of emotional self-descriptors (5 and 10 weeks post randomisation) relative to SHE
- a. Decreased reaction time to identify positive compared with negative characteristics in Emotional Categorisation Task (ECAT)

- 3. dCBT-I will increase positive emotional memory bias relative to SHE (5 and 10 weeks post randomisation)
- a. Increased memory for positive compared with negative words in the Emotional Memory Task (EMEM)
- 4. dCBT-I will reduce self-reported emotion regulation deficits (Difficulty with Emotion Regulation Scale, DERS), worry (Penn State Worry Questionnaire, PSWQ) and perseverative thinking (Perseverative Thinking Questionnaire, PTQ) (5 and 10 weeks post randomisation) relative to SHE
- 5. dCBT-I will reduce self-reported depression severity (Patient Health Questionnaire, PHQ-9) (5 and 10 weeks post randomisation) relative to SHE
- 6. dCBT-I will reduce insomnia severity (Insomnia Severity Index, ISI) (5 and 10 weeks post randomisation) relative to SHE
- 7. Change in emotional perception of faces (FERT: Changes in recognition accuracy for happy and sad facial expressions) at week 5 will mediate change in depressive symptoms (PHQ-9) at week 10
- 8. Change in emotion processing (ECAT: reaction times for positive compared with negative words) at week 5 will mediate change in depressive symptoms (PHQ-9) at week 10.
- 9. Change in self-rated emotion regulation, worry and preservative thinking (reductions in DERS, PSWQ and PTQ scores) at week 5 will mediate the effect of dCBT-I over SHE on depressive symptoms (PHQ-9) at week 10
- 11. dCBT-I will increase the level of morningness (Munich ChronoType Questionnaire, MCTQ) (5 and 10 weeks post randomisation) relative to SHE
 - a. Earlier midpoint of sleep on work-free days, sleep-corrected (MSF SC)
- 10. dCBT-I will increase positive affect (Positive and Negative Affect Schedule Short Form Positive affect, PANAS-SF: PA) and reduce negative affect (Positive and Negative Affect Schedule Short Form Negative affect, PANAS-SF: NA) (5 and 10 weeks post randomisation) relative to SHE
- 12. Change in level of morningness (MSF SC from MCTQ) at week 5 will mediate change in depressive symptoms (Patient Health Questionnaire, PHQ-9) at week 10

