If post randomisation variables, such as compliance with treatment, or baseline variables are found to be predictive of non-completion of outcome, such that it would not be suitable to adjust for them in the main analyses, then multiple imputation will be considered.

Handling outliers

Any outliers will be checked and verified to ensure that they are true values. Outliers will be identified as those observations more than four standard deviations from the mean. Once they have been confirmed, a sensitivity analysis will be carried out to assess the impact of these values on the results by excluding these participants (see below).

Multiple comparisons and multiplicity

The primary outcome is clearly stated in the protocol. Due to the use of 2 primary outcomes (accuracy for sad and happy faces, respectively) 0.05/2 = 0.025 will be considered significant for the main analysis.

Model assumptions

Standard residual diagnostics, such as inspection of the histogram of the residuals, will be used to assess the appropriateness of the model. If assumptions are violated we will consider firstly using the change in accuracy from baseline as the dependent variable. If the assumptions are still violated we will consider alternative non- parametric approaches.

Secondary analysis

Secondary outcomes

Continuous secondary outcomes will be analysed in the same way as the primary outcome. We will test the hypothesis for between-group difference in the outcomes at 5 weeks and 10 weeks using mixed effects models with baseline outcome measure, treatment assignment, assessment time, stratification variables and a treatment by time interaction as fixed effects with a subject-varying random intercept. We will apply standard regression diagnostics. The proposed analysis assumes that these secondary outcomes are continuous and satisfy the assumptions of the mixed effects model. Where these assumptions are not satisfied, the data will be transformed or if a transformation is not possible, a non-parametric approach to analysing the data will be adopted.

The secondary outcomes include:

Self-rated

The Difficulties in Emotion Regulation Scale (DERS), total score

The Patient Health Questionnaire (PHQ9)

The Penn State Worry Questionnaire PSWQ-Past Week (The PSWQ-PW)

The Perseverative Thinking Questionnaire (PTQ)

Insomnia Severity Index (ISI)

Mood Instability (one self-rated item from the Structured Clinical Interview for DSM-IV (SCID-II))

Munich Chronotype Questionnaire (MCTQ)

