Change in level of morningness (MSF SC from MCTQ)

Change in mood (PANAS-SF, positive and negative affect)

If the efficacy analysis shows significant between-group differences in these measures at 5 and 10 weeks, modern causal inference methods will be used to investigate the mediation hypotheses. Parametric regression models will be employed to test for the indirect effect of emotion regulation/processing/morningness/mood at week 5 on depression severity (PHQ-9) at 10 weeks. Since all the measures are continuous, the indirect effects are calculated by multiplying relevant pathways and bootstrapping is used to produce valid standard errors for the indirect effects. Results will be presented as indirect effects with 95% bootstrapped percentile CIs and also as percentage of the total effect that is mediated. All analyses will adjust for baseline measures of the mediators. An adjusted model, including the stratification variables will also be presented. Mediation analyses are potentially biased by measurement error in mediators and hidden confounding between mediators and outcomes and we will investigate the sensitivity of the estimates to these problems.

CACE analysis

A complier-average causal effect (CACE) analysis of the primary outcome will be carried out to determine what effect the level of compliance to the intervention has on the treatment effect i.e. an estimate of the treatment effect amongst compliant patients. Descriptive statistics will be presented for the primary outcome in the control group, and in the intervention group split by the number of Sleepio sessions attended (i.e. 0,1,2,3, 4, 5, 6).

Baseline characteristic of the participants by compliance status will be reported. Statistical testing of baseline characteristics with compliance will be carried out to determine factors associated with compliance. A table of baseline characteristics by control, complier and non-complier with statistical comparison between compliers and non-compliers in the CBT-I intervention arm will be reported.

To obtain an unbiased estimate of the effect of compliance to the intervention on treatment effect, we will produce the complier-average causal effect estimates of the difference between the mean accuracy scores for sad and happy faces (FERT) for the compliers in the Sleepio group compared to the would be

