compliers in the control group (CACE). For the primary CACE analysis, a sufficient level of adherence will be defined as completing at least 3 Sleepio sessions. The analysis will be performed using a two stage residual inclusion regression with randomisation as an IV. In the first stage, a regression of treatment receipt on randomisation will be conducted. In the second stage, a regression of the outcome on treatment receipt will be conducted, adjusting for the first-stage residual as covariates, as well as the same covariates as the intention-to-treat analysis. Bootstrapping will be used to obtain CI due to the two stage approach.

Exploratory analysis

Exploratory analyses will be conducted to assess the effect of dCBT-I on other expressions in the FERT (fear, anger, disgust, surprise, neutral), including the grouping of positive (happy, surprise) vs negative (fear, anger, disgust) expressions. We will also report and conduct exploratory analyses on reaction times and emotion misclassifications from the FERT. Emotion Misclassification is defined as the percentage of misclassifications for each emotion (Number of responses to each emotion when that emotion not displayed/Number of faces of all other expressions). Emotion reaction time is the calculated mean reaction time for correct responses for each emotion (if no correct responses, recorded as a missing value).

For the secondary objective tasks (ECAT, EMEM), we will further report and analyse % accuracy and % of misses (ECAT) and misclassifications of each condition (positive or negative words) and mean reaction time for correct responses for each condition (positive and negative words) (EMEM).

We will report sleep diary data collected as part of the dCBT-I treatment (in the intervention group) and also report % of participants scoring < 11 on the ISI and < 10 on the PHQ-9 after treatment, to provide a clinical context.

Possible predictors of treatment effects on the FERT will be analysed and reported. Specifically, we will investigate early/late chronotype, self-rated emotion regulation, high vs low depression scores (PHQ-9 dichotomised at 15) and worry as predictors of responses. Moderators will be assessed separately by repeating the primary analysis model and including an interaction term between randomised treatment and the moderator.

Sensitivity analysis

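### The MSFsc formula has no condition, so anyone who sleeps less on work-free days than on work days is scored later than their observed midpoint, although they have no free-day catch-up sleep to remove

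*Combined protocol and SAP*

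**What the plan says.** The only scoring rule is in the protocol, under Secondary Outcome measures (self-reported), in the entry for the Munich Chronotype Questionnaire. MSFsc "is calculated from the midpoint of sleep on work-free days", and the correction then applied to that midpoint reads: "minus half of the difference between sleep duration on work-free days and average sleep duration of the week to control for sleep debt". The sentence does not say which duration must be the longer, and it gives no alternative for people who sleep less on free days.

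The SAP uses the variable without deriving it:

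- Aim and hypotheses, secondary hypothesis 11a, predicts "Earlier midpoint of sleep on work-free days, sleep-corrected" under dCBT-I at 5 and 10 weeks. The protocol has the matching hypothesis 9.
- Secondary outcomes lists only the instrument, "Munich Chronotype Questionnaire (MCTQ"). The model there includes the baseline value of each outcome as a fixed effect.
- Mediation analysis lists "Change in level of morningness (MSF SC from MCTQ") at week 5 as a possible mediator of week-10 PHQ-9.
- Exploratory analysis states that "we will investigate early/late chronotype, self-rated emotion regulation" and other variables will be examined as predictors of the FERT effect. It does not say how early and late are defined.

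**The concern.** The stated reason for the correction is sleep debt. Someone who catches up on free days sleeps longer then, and this pushes the free-day midpoint later, so half of the excess is subtracted. The reasoning needs an excess. When free-day sleep is the shorter, the bracket is negative, subtracting it adds time, and the participant is recorded as a later type than their reported sleep shows. Taking the difference as an absolute value does not help: it moves the same person earlier for a debt that they do not show.

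At stake is the accuracy of MSFsc as a directional secondary outcome, as a baseline covariate and as a week-5 mediator, and possibly the early/late grouping. Treatment could plausibly change the gap between work-day and free-day sleep, since the protocol's description of dCBT-I includes sleep restriction and an agreed sleep schedule. An error tied to that gap therefore need not cancel between the arms.

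**Working it through.** The plan gives no figure for this point, so there is none to reproduce. The check is algebra on the protocol's formula, followed by examples whose durations, midpoints and work-day counts are assumptions.

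**Formula.** Let WD be work days per week, SDw and SDf sleep duration on work and work-free days, and MSF the observed free-day midpoint.

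- Weekly mean: SDweek = [WD × SDw + (7 − WD) × SDf] / 7
- Plan: MSFsc = MSF − 0.5 × (SDf − SDweek)
- Since SDf − SDweek = (WD/7) × (SDf − SDw), it follows that MSFsc − MSF = (WD/14) × (SDw − SDf)

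For WD > 0 the shift is later than observed exactly when SDf < SDw.

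**Shift per hour of gap (60 × WD/14):**

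| Work days | Minutes later per hour |
|---|---|
| 3 | 12.9 |
| 4 | 17.1 |
| 5 | 21.4 |
| 6 | 25.7 |

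**Examples (MSF 4:00, 5 work days):**

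- *Catch-up sleeper, SDw 6 h, SDf 8 h.* SDweek = (30 + 16)/7 = 6.571 h. Correction = 0.5 × 1.429 h = 42.9 min, giving 3:17. This is the intended case.
- *Shorter free-day sleeper, SDw 7 h, SDf 6 h.* SDweek = (35 + 12)/7 = 6.714 h. Correction = 0.5 × (−0.714 h) = −21.4 min, giving 4:21. An absolute difference would give 3:39. With the condition proposed below, the score is 4:00.
- *Same person at follow-up, SDw 7 h, SDf 7 h, MSF still 4:00.* The score is 4:00. From 4:21 this is an apparent advance of 21.4 min (12.9 to 25.7 min for 3 to 6 work days) with no change in observed timing.

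**Possible effect on the arm contrast.** The documents give no distribution of SDf − SDw. Assume it is normal with 5 work days. The mean late shift in an arm is then 60 × (5/14) × E[max(SDw − SDf, 0)] minutes, and the artefact is the dCBT-I value minus the SHE value (positive means later).

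- *Same SD in both arms (0.75 to 1.5 h), SHE mean 0.5 to 1 h, dCBT-I mean 0 to 0.25 h:* artefact +1.7 to +8.0 min.
- *Smaller SD under dCBT-I, as would follow if treatment makes sleep more regular:*

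| SHE mean/SD (h) | dCBT-I mean/SD (h) | dCBT-I − SHE (min) |
|---|---|---|
| 0.5/1.5 | 0.25/0.5 | 2.12 − 8.17 = −6.05 |
| 0.5/1.5 | 0/0.5 | 4.27 − 8.17 = −3.90 |
| 1/1.5 | 0.25/0.5 | 2.12 − 4.86 = −2.74 |
| 1/1 | 0/0.5 | 4.27 − 1.79 = +2.48 |

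The sign changes with the assumed spread. These sums also ignore the adjustment for baseline MSFsc.

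**The case against.** The strongest defence is that the formula is a coherent symmetric rule. Since MSF is free-day sleep onset plus SDf/2, MSFsc = onset + SDf/2 − SDf/2 + SDweek/2 = onset + SDweek/2. Everyone is standardised to their own weekly average, and a person who sleeps less on free days can be seen as under-sleeping then and recovering on work days. That is a legitimate alternative convention, and it makes the point less certain. It does not fit well with the purpose that the protocol states, which is control of sleep debt in a free-day midpoint. If a symmetric standardisation is meant, the plan should say so.

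A second objection is that the protocol's sentence only summarises a named instrument and points to Appendix 5j, which is not in the supplied text. A conditional rule may stand there. That cannot be excluded; if it does, the body text still needs reconciling with it.

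A reader might also infer that the rule biases the comparison against the hypothesis: dCBT-I evens out sleep across the week, so more dCBT-I participants would take the late shift. The documents do not support this. At a gap of zero the shift is zero, and more regular sleep reduces the spread of the gap as well as its mean. The calculations above give artefacts in both directions, and the 7/6 h to 7/7 h example moves towards the hypothesis.

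**Conclusion.** The point holds as a minor one. As written, the rule moves MSFsc later than the observed midpoint for every participant with shorter free-day than work-day sleep, by (WD/14) × the gap: about 21 min per hour with 5 work days. This follows from the protocol's own formula, with the difference read as signed. Calling it an error rests on the stated sleep-debt purpose and on there being no conditional rule in Appendix 5j.

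The documents do not show how many participants are affected, or the size or direction of any distortion between the arms. The illustrative range of roughly 6 min early to 8 min late reflects the chosen assumptions and is not an estimate. Reach is limited to one secondary outcome with its baseline covariate, a mediation analysis run only if the efficacy results are significant, and the exploratory early/late grouping if that is cut from MSFsc. The primary FERT outcome, its alpha and the sample size are unaffected.

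**What to change.** Write the derivation into the SAP:

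- If free-day sleep exceeds work-day sleep, MSFsc = MSF − 0.5 × (free-day sleep − weekly mean sleep).
- Otherwise, MSFsc = MSF.

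Apply it at baseline, week 5 and week 10, in the mediator, and in the early/late chronotype grouping if that is based on MSFsc. Report the unconditional formula as a sensitivity analysis, and check that Appendix 5j agrees with the rule adopted. Scores of participants with longer free-day sleep do not change.

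The cost is one line of SAP wording and one condition in the derivation code, with no new data. Settling it before analysis also avoids a later choice between two scoring rules.

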Appendix 5k)			
ECAT	X	X	X
EMEM	X	X	X
Audit of engagement		Х	Х
with mental health			
services and sleep			
medication			
(Appendix 5i)			
Device Monitoring	X	X	X
Question(s)			
(Appendix 5a)			

Fig 2: Standard Protocol Items: Recommendations for Interventional Trials (SPIRIT) figure.

Randomisation and allocation concealment

Randomization will be performed independently from the study team through the ePRO system. This study will use stratified randomisation with an allocation ratio of 1:1, as recommended for small scale clinical trials (Kernan et al., 1999). Randomisation and stratification according to sex (male/female), age (25-44, 45-65), depression severity (PHQ-9 Scores: $\leq 15: \geq 16$) and insomnia severity (ISI scores $\leq 19: \geq 20$). On completion of baseline measures each participant will be randomly assigned to either dCBT-I or SHE. The team will be unable to influence randomization in the ePRO system, but will manually contact the participant to inform them of their allocation.

Blinding and bias

Self-report assessments and performance tasks will be completed entirely online. Participants will be informed of their randomisation outcome (dCBT-I or SHE, referred to as sleep treatment 1 and 2 in the PIS) and will not be blind to treatment allocation. To minimise bias, the PIS will not explicitly reveal that SHE is used as a minimal control.

End of study

The end of study is defined as the last participants completed the last assessment (10 weeks).

Sample size calculation

Our planned primary intention-to-treat analysis will compare dCBT-I versus SHE for objective biases in negative emotional processing of faces at week 10. Our desired sample size of n=200 and an estimated attrition rate of 20% (based on recently completed trials (Kyle et al., 2017)), will be powered to detect a minimum between group standardized effect size of 0.5 at week 10, with a power of 90% and a two-tailed α of 0.05.

Recruitment and payment

The study will recruit through multiple channels. These may include online (e.g., Social media, mental health charity websites), print and broadcast media advertisements, and the use of contact lists where adults who have agreed to be contacted about future studies will be notified about the trial, (including Sleepio mailing lists). See **appendices 4, 9** and **10.** In addition to receiving free access to the dCBT-I program, participants will also receive payment in the form of Amazon™ gift vouchers for completing each post-randomisation assessment point (£10 for mid treatment, £15 for post-treatment).

Assessment of safety

The likelihood of serious adverse events occurring during this trial is low since CBT-I (in any format) has not been reported to cause them. The intervention offered in the trial has previously been tested in > 10 randomised trials and no SAEs related to the intervention have been reported (Beattie et al., 2015; C. A. Espie et al., 2001, 2007, 2008, 2012, 2013; Freeman, Sheaves, et al., 2015; Henry et al., 2020). Moreover, clinical evaluation in patients with anxiety disorder and depression revealed no evidence of SAEs (Gratz & Gunderson, 2006). Since the trial is completed online, with limited formal participant contact, we are unlikely to become aware of all potential adverse events. However, should we do so, we will define serious adverse events as: (1) death, (2) suicide attempt, and (3) admissions to secure units.

Given the relationship between improved sleep quality and reduced suicidal ideation (Trockel et al., 2015), we do not expect any increase in suicidal ideation amongst the intervention group. Conversely, it is likely that we may observe reductions in suicidal ideation in the intervention arm. Nonetheless, suicidal ideation will be assessed at each point in both arms using item 9 of the PHQ-9 and participants who demonstrate frequent suicidal ideation (score >1) will be prompted with an automatically triggered email, sign-posting to appropriate support (see **appendix 4, section 7** and **appendix 11**). While we screen out people with suicidal ideation on study entry (using criterion described in screening section: C-SSRS responses), we will not remove participants who report suicidal ideation during the course of the trial. Should a participant report significant emotional distress (including suicidal thinking) to the research team, an experienced psychiatrist will be available to support and advise, and where necessary speak directly to the participant.

Stop-go pilot phase

In light of the low treatment adherence in our previous study (The SLEEPER study, CUREC ethics approval reference R55815), we will perform a stop-go pilot phase in an initial group of 50 participants (n=25 in each arm). Data on treatment adherence and completion of assessments will be evaluated in these participants and the trial team will consider stopping the trial if treatment adherence, defined as logging in to at least one session on Sleepio, is lower than 66% in the CBT-I arm. Should this criterion be met the trial will continue to recruit the remaining 150 participants; the 50 pilot participants will be included in the final analyses.

Data management

Access to Data

Participant information will be kept strictly confidential. Electronic data will be de-identified with a code and such data will be kept on firewall and password-protected computers. An electronic linking file will enable identification by matching the study ID to the participant name; this file will be encrypted and stored

securely in a separate folder. This linking file will be destroyed at the end of the study. Responsible members of the University of Oxford may be given access to data for monitoring and/or audit of the study to ensure compliance with regulations.

Data Recording and Record Keeping

The chief investigator will be responsible for data management and archiving. Data quality will be maintained through adherence to the University of Oxford's Policy on the Management of Research Data and Records. We will seek to collect screening questionnaires electronically using the Qualtrics® Survey platform online. All other questionnaire and performance task data will be collected and securely stored online using the P1vital® ePRO system. These data will be encrypted before being transferred to the research group for analysis. P1Vital will store study data until deletion is requested by the chief investigator. This will take place after the study has terminated and all relevant data has been transferred to the research group. Participants email addresses and any other personal information will be deleted from the system at the end of the study. A data agreement will be put in place between P1vital® and the University of Oxford for the purposes of delivering this service. As part of this agreement P1Vital reserve the right to use the anonymised emotional processing task data (FERT, ECAT, EMEM) and basic demographic data such as gender & age (unattached to names or identifiable information) for internal, non-commercial research purposes. This will be made clear in the PIS.

Data collected from potential participants who do not go on to enrol in the study will be stored until the end of the study and then destroyed. Participants' personal information (e.g., email address, phone number) will be retained until either a summary of the study results has been sent to participants, or 12 months has passed since the end of study, whichever comes first.

Sleepio data

The Big Health team will supply Sleepio access codes. The study team will then provide each of the study participants with one access code for Sleepio®. The Sleepio® programme requires participants to register via this access code to use the system, inputting their personal data including identifiers. This is the usual procedure for all users of this programme. The Sleepio® programme has its own privacy policy that can be accessed here: https://www.Sleepio.com/privacy/.

The Big Health team will send the research team information on the number and date of completed Sleepio sessions for each participant (linked to their access code) as well as completed sleep diaries during the treatment. This information will be sent in an encrypted, password-protected spreadsheet and will not include any personally identifiable information. This will be made clear to participants in the PIS.

Data sharing

For increased reproducibility we aim to publish a fully anonymised data set in an open repository after the study has been completed and main results reported. We will make this clear in the PIS and ask participants to consent to this use of their research data.

Statistical analysis

In accordance with Consolidated Standards of Reporting Trials (CONSORT) guidelines, we will record and report all participant flow (Moher 2010) in addition to providing descriptive statistics of recruitment, dropout, and completeness of interventions. The main efficacy analysis will be conducted on an intentionto-treat basis including all participants. Baseline characteristics will be presented by randomization. We will then test the hypothesis for between-group change in the primary and secondary outcomes at 5 weeks and 10 weeks using analysis of covariance with baseline outcome measure and treatment assignment as fixed effects, and apply standard regression diagnostics. The analysis will use statistical techniques for handling missing outcome data under a missing-at random assumption. If the efficacy analysis shows significant between-group differences in the subjective and objective emotion processing measures at 5 and 10 weeks, modern causal inference methods will be to investigate the mediation hypotheses. Parametric regression models will be employed to test for the indirect effect of emotion regulation/processing at week 5 on depression severity (PHQ-9) at 10 weeks. Since all the measures are continuous, the indirect effects are calculated by multiplying relevant pathways and bootstrapping is used to produce valid standard errors for the indirect effects. All analyses will adjust for baseline measures of the mediators, outcomes and putative measured confounders. Mediation analyses are potentially biased by measurement error in mediators and hidden confounding between mediators and outcomes and we will investigate the sensitivity of the estimates to these problems.

Dissemination

